**Treatment Groups and Duration:**

Study RHBX has 3 treatment groups during the 52-week Blinded Treatment Dosing Period: 80 mg ixekizumab Q4W, 80 mg ixekizumab Q2W, and placebo at a 1:1:1 ratio. In each ixekizumab treatment group, half of the patients will receive an 80-mg starting dose and half a 160-mg starting dose (1:1 randomization). Randomization will be stratified by country and screening MRI/CRP status (positive MRI and elevated C-reactive protein [CRP]; positive MRI and nonelevated CRP; negative MRI and elevated CRP). All doses are administered via SC injection. At baseline (Week 0), all patients will receive 2 injections. Patients assigned to an ixekizumab treatment regimen with a 160-mg ixekizumab starting dose will receive 160 mg of ixekizumab as two 80-mg SC injections. Patients assigned to an ixekizumab treatment regimen with an 80-mg starting dose will receive 80 mg of ixekizumab as 1 SC injection and 1 SC injection of placebo. Patients assigned to the placebo treatment group will receive 2 SC injections of placebo. After Week 0 and through Week 50, all patients will receive 1 injection every 2 weeks.

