## 5.2. Determination of Sample Size

Approximately 300 patients will be randomized at a 1:1:1 ratio in the Blinded Treatment Dosing Period (Period 2) to ixekizumab 80 mg Q2W, ixekizumab 80 mg Q4W, and placebo. With 100 patients per treatment group, this study will have approximately 98% power to test the superiority of ixekizumab Q2W to placebo for the ASAS40 at Week 16. The following assumptions were used for the power calculations for ASAS40 response rates at Week 16 regardless of starting dose: 46% for ixekizumab 80 mg Q2W treatment group and 18% for the placebo group. A 2-sided Fisher's exact test at the 0.05 level is assumed. These assumptions are based on the data from historical clinical studies in nonrad-axSpA patients with objective signs of inflammation (etanercept, adalimumab, certolizumab, and golimumab [Sieper et al. 2013; Dougados et al. 2014; Landewé et al. 2014; Sieper et al. 2015]).

There is little data from similarly designed 52-week placebo-controlled trials regarding the ASAS40 response rate for active and placebo treated patients to guide power estimation at Week 52. [Table RHBX.5.1](#) provides power estimates to test the superiority of ixekizumab Q2W to placebo for the ASAS40 at Week 52, assuming various ASAS40 response rates for ixekizumab Q2W and placebo at Week 52. A 2-sided Fisher's exact test at the 0.05 level is assumed.

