## 5.3. Method of Assignment to Treatment

Patients who meet all criteria for enrollment will be randomized to double-blind treatment at Week 0 (Visit 2). Assignment to treatment groups will be determined by a computer-generated random sequence using an interactive web-response system (IWRS). The IWRS will be used to assign double-blind investigational product to each patient. Site personnel will confirm that they have located the correct investigational product package by entering a confirmation number found on the package into the IWRS.

To achieve between-group comparability, the randomization will be stratified by country and screening MRI/CRP status (positive MRI and elevated CRP; positive MRI and nonelevated CRP;

negative MRI and elevated CRP). Elevated CRP is defined as  $>5.00$  mg/L. Due to operational feasibility, stratification by CRP is based on the CRP value at Screening.

Target enrollment will be a minimum of approximately 20% for each of the MRI/CRP strata. Once a specific stratum is fully enrolled, the sponsor may stop further enrollment of patients fitting the criteria of that stratum.

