## **6.1.2. General Considerations for Analyses during the Blinded Treatment Dosing Period (Period 2)**

### **6.1.2.1. Intent-to-Treat Population and Safety Population**

Period 2 starts at the first injection of study treatment at Week 0 (Visit 2) and ends on the date of Week 52 (Visit 15) or the early termination visit (ETV; between Weeks 0 and 52). For patients who were deemed as inadequate responders by their investigators and were treated with biologic rescue of ixekizumab 80 mg Q2W, only data up to the time of initiation of biologic rescue of ixekizumab 80 mg Q2W will be included in the Period 2 analyses using the ITT and Safety Populations. These patients will be considered nonresponders to categorical assessment per the nonresponder imputation (NRI) method after initiation of biologic rescue with ixekizumab 80 mg Q2W. Data collected after biologic rescue therapy has started will be summarized separately for the IR Population (Section 6.1.2.2).

Baseline for ITT and Safety Populations will be defined as the last available value before the first injection for efficacy, health outcomes, and safety analyses. In most cases, this will be the measure recorded at Week 0 (Visit 2). For efficacy measures, if the patient does not take any injection, the last available value on or prior to randomization date will be used. Change from baseline (CFB) will be calculated as the visit value of interest minus the baseline value. For safety analyses using a baseline period, the baseline period is defined as the time from Visit 1 to the date/time of the first injection.

Comparisons between each initially randomized ixekizumab treatment group (80 mg Q2W or 80 mg Q4W) and initially randomized placebo will be performed for all analyses in Period 2.

The randomization to treatment groups is stratified by country and screening MRI/CRP status (positive MRI and elevated CRP; positive MRI and nonelevated CRP; negative MRI and elevated CRP) as described in Protocol Section 6.2. The countries will be categorized into geographic regions for analysis. Geographic regions are defined in Table RHBX.6.3. Unless otherwise specified, the statistical analysis models will adjust for geographic region and screening MRI/CRP status.

Screening MRI and CRP status included in all the analysis models for Period 2 is determined based on the MRI readings and central lab CRP values obtained at screening visit (Visit 1).

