The impact of ixekizumab starting dose of 160 mg versus 80 mg on treatment response at Week 16 will be summarized and evaluated. Response rates in selected categorical variables (ASAS40/20, ASDAS<2.1, BASDAI50, ASDAS clinical important improvement, ASDAS major improvement) and LS mean change in selected continuous efficacy and health outcome measures (CRP, BASFI, BASDAI, spinal pain and SF-36 PCS) at Weeks 16 and 52 will be presented for patients randomized to ixekizumab Q2W or Q4W treatment regimen with ixekizumab 160 mg starting dose and with ixekizumab 80 mg starting dose.

For response rates, starting dose comparisons within ixekizumab Q2W or Q4W treatment regimens will be based on logistic regression model with treatment, starting dose, and treatment-by-starting-dose interaction (only ixekizumab Q2W and Q4W will be included in the analyses). Starting dose comparison combining ixekizumab Q2W and Q4W treatment regimens will be based on logistic regression model with only starting dose in the model.

For mean change analysis, starting dose comparisons within ixekizumab Q2W or Q4W treatment regimens will be based on MMRM model with treatment, starting dose, baseline value, visit, baseline value-by-visit, treatment-by-visit, treatment-by-starting dose, starting dose-by-visit, and treatment-by-starting dose-by-visit interactions as fixed factors. Starting dose comparison combining ixekizumab Q2W and Q4W treatment regimens will be based on MMRM model with starting dose, baseline value, visit, baseline value-by-visit, and starting dose-by-visit interaction as fixed factors. The differences in response rates and LS mean changes between starting doses and the corresponding 95% CI will be reported as well.

For variables that are not collected at each postbaseline visit, data may exist at visits where the variable was not scheduled to be collected, due to early discontinuation visits. In these situations, data from the early discontinuation visit that do not correspond to the planned collection schedule will be excluded from the MMRM and categorical MMRM analyses (Andersen and Millen 2013). However, the data will still be used in other analyses, including shift analyses, change from baseline to modified baseline observation carried forward (mBOCF) endpoint analyses, and other categorical analyses.

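### The starting-dose models leave out region, screening MRI/CRP status and, when pooled, regimen; the comparison is unbiased but mildly conservative if those factors are prognostic

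*SAP*

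**What the plan says.** The default in SAP Section 6.1.2.1 is: "Unless otherwise specified, the statistical analysis models will adjust for geographic region and screening MRI/CRP status". Section 6.2 and Protocol Section 9.2.1 repeat it, and the main logistic, MMRM, ANCOVA and proportional-odds models follow it. On assignment, SAP Section 5.3 says that "the randomization will be stratified by country and screening MRI/CRP status". The Protocol synopsis and Protocol Section 6.1 add that starting dose is randomised 1:1 within each ixekizumab regimen.

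The same SAP section then gives four models for starting dose:

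- Response, within regimen: regimen, starting dose and their interaction.
- Response, regimens pooled: the comparison "will be based on logistic regression model with only starting dose in the model".
- Mean change, within regimen (MMRM): regimen, starting dose, baseline value, visit and interactions.
- Mean change, regimens pooled (MMRM): starting dose, baseline value, visit and interactions.

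None contains region or MRI/CRP status, and neither pooled model contains regimen. No reason is stated. Differences in response rates and in least-squares mean changes are to be reported with 95% confidence intervals. Table RHBX.6.5 labels the starting-dose response analysis just as it labels the primary analysis (logistic regression with NRI), so the change of covariates is easy to miss.

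**The concern.** When allocation is balanced on prognostic factors and the model then ignores them, the between-stratum variation that the design removed is still counted as noise. The model-based standard error of a mean or rate difference overstates the true sampling variation, and the test rejects too rarely under the null.

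Starting dose is a deliberate design feature: Protocol Sections 4.3 and 4.4 say that the active patients are split in half so that its impact can be evaluated. About 100 v 100 patients are available pooled and 50 v 50 within a regimen, and no power is stated. At stake is some sensitivity to a real difference between starting doses, given up for no stated gain.

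**Working it through.** **1. The plan's own figure.** The only power statements concern ixekizumab Q2W against placebo: "46% for ixekizumab 80 mg Q2W treatment group and 18% for the placebo group", 100 per group, two-sided Fisher's "exact test at the 0.05 level is assumed". Exact enumeration gives 98.8% against the stated 98%. The six Week 52 rows also reproduce: 100.0, 99.9, 93.5, 100.0, 97.4 and 66.9% against 99, 99, 93, 99, 97 and 66%. Nothing is stated for starting dose, so the rest rests on assumptions.

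**2. Inputs.** From the documents: 300 patients at 1:1:1; starting dose 1:1 within regimen; 15 countries (8 European, 7 not, SAP Table RHBX.6.3) by 3 MRI/CRP strata. Assumed: permuted blocks of 6, equal country sizes, stratum shares of 40/30/30% (compatible with the target minimum of about 20% each), an overall response rate of about 42%, and every covariate effect. The pooled model was fitted as written and again with regimen, region and MRI/CRP status added (1 + 1 + 2 = 4 extra parameters).

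**3. Response**, 4,000 trials per setting. The assumed odds ratios are for highest against lowest MRI/CRP stratum, region and regimen. Power is at a starting-dose odds ratio of 2.

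| Assumed ORs | Type I error, as written | Type I error, adjusted | Power, as written | Power, adjusted |
|---|---|---|---|---|
| 1, 1, 1 | 0.051 | 0.054 | 67.5% | 68.1% |
| 2, 1.5, 1.2 | 0.044 | 0.049 | 63.9% | 66.0% |
| 3, 2, 1.5 | 0.042 | 0.050 | 59.8% | 63.7% |
| 5, 2, 1.5 | 0.037 | 0.049 | 57.1% | 62.4% |

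The simulation error of a type I error near 0.05 is sqrt(0.05 x 0.95 / 4000) = 0.003, so the weakest prognostic setting alone would not settle the matter; the trend does.

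**4. Where the loss appears for response** (ORs 3, 2, 1.5).

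- *Odds ratio.* With a true starting-dose odds ratio of 2, the mean log odds ratio is 0.645 as written and 0.717 adjusted, with standard errors 0.292 and 0.309. The unadjusted standard error is the smaller one, but the ratios are 0.645/0.292 = 2.21 and 0.717/0.309 = 2.32. Attenuation outweighs the smaller standard error.
- *Rate difference, no starting-dose effect.* The usual model-based standard error is sqrt(2 x 0.42 x 0.58 / 100) = 0.0698. The actual sampling SD is 0.0671 as written and 0.0667 adjusted. The ratio 0.0698/0.0671 = 1.04 predicts a type I error of 2 x (1 - Phi(1.96 x 1.04)) = 0.041, close to the simulated 0.042.

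**5. Mean change.** This was checked with a linear model at one time point. If the omitted terms are perfectly balanced and explain a share R2 of the variance left, the standard error is inflated by 1/sqrt(1 - R2), and the type I error is 2 x (1 - Phi(1.96/sqrt(1 - R2))). Power is simulated for a difference of 0.4 SD, 6,000 trials per setting.

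| R2 (assumed) | SE inflation | Type I error, formula | Type I error, simulated | Power, as written | Power, adjusted |
|---|---|---|---|---|---|
| 0 | 0% | 0.050 | 0.053 | 78.9% | 78.6% |
| 0.05 | 2.6% | 0.044 | 0.040 | 80.1% | 81.3% |
| 0.10 | 5.4% | 0.039 | 0.046 | 81.3% | 84.3% |
| 0.20 | 11.8% | 0.028 | 0.033 | 82.5% | 88.3% |

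**6. If balance is poor.** There are 15 x 3 = 45 cells for about 300 patients, or 300/45 = 6.7 per cell, and no block size is given. Under simple randomisation (ORs 3, 2, 1.5), type I error is 0.046 with either model, so the conservatism goes. The sampling SD of the rate difference is then 0.0699 as written and 0.0673 adjusted, a true but small loss of precision.

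**7. Not simulated.** The 50 v 50 within-regimen models and the full repeated-measures model were not run. The formula in step 5 does not depend on sample size, so for mean change the same relative inflation applies within a regimen, for the two factors omitted there.

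**The case against.** The strongest reply has four parts.

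- *The choice is permitted.* The default carries its own exception, and the starting-dose paragraphs use it. That stands: this is a prespecified departure, not a contradiction.
- *It is not unusual in this SAP.* A reader might infer that every other Period 2 efficacy model adjusts. The documents do not support that: the efficacy subgroup models (Section 6.15.1), the ADA-by-efficacy model (Section 6.13.8.2.2) and the Fisher's exact tests also omit these factors. The contrast is only with the main treatment-comparison models. Nor is this the trial's smallest comparison: 100 v 100 equals the planned primary comparison, and some subgroups tested are smaller than 50 v 50.
- *A one-factor model gives the marginal rate difference directly.* That is true and is a convenience, but standardising an adjusted model gives the same estimand.
- *The size is assumed.* This also stands. No document says how strongly region, MRI/CRP status or regimen predicts response, and baseline value in the MMRM already absorbs some of their effect.

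None of this shows a benefit from leaving the factors out. With about 200 ixekizumab patients, four extra parameters are easily supported.

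**Conclusion.** The omission is real, unexplained and minor. If the factors are prognostic, the pooled tests as written have type I error of about 0.037 to 0.044 for response and about 0.03 to 0.044 by formula for mean change (0.033 to 0.046 simulated). They give up about 2 to 5 and 1 to 6 points of power respectively. These figures rest on the assumed covariate effects, response rate and block size, and on allocation reasonably balanced within strata. With no prognostic effect, the two models agree within simulation error.

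Two stronger readings should be resisted. A reader might infer that leaving out regimen confounds the pooled comparison; it does not, because starting dose is randomised 1:1 within regimen, so the null test and the rate difference are unbiased. A reader might also infer that all standard errors are too large. That holds for mean change and for the model-based standard error of the rate difference, but not on the log-odds scale, where the loss comes from attenuation.

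SAP Section 4 lists the starting-dose objective as one to explore, and Section 6.10.4 applies no multiplicity control. No primary or alpha-controlled result is affected.

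**What to change.** In SAP Section 6.1.2.1, add geographic region and screening MRI/CRP status to all starting-dose logistic and MMRM models, and add regimen to the two pooled models.

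Keep the response-rate difference with its 95% confidence interval, standardised: from the adjusted model, average the predicted response over all ixekizumab patients under each starting dose, take the difference, and obtain the interval by the delta method or bootstrap. Name the covariates in the starting-dose rows of Table RHBX.6.5. If the sponsor prefers the present models, one sentence should say why.

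The cost is SAP wording and a little programming, settled before unblinding. No new data are needed.

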#### **6.1.2.2. Inadequate Responder Population**

The treatment period for biologic rescue of ixekizumab 80 mg Q2W starts at the time of first injection of biologic rescue of ixekizumab 80 mg Q2W on or after Week 16 (Visit 8) and ends at the date of study treatment discontinuation for patients who did not initiate other biologic therapy, or at the start of other biologic treatment for patients who initiated other biologic therapy.

The treatment period for other biologic rescue (excluding ixekizumab 80 mg Q2W) starts at the time of first injection of other biologic rescue and ends on the date of Week 52 (Visit 15) or the ETV/last regularly scheduled visit.

For efficacy analyses on the IR Population, baseline is defined as the last nonmissing assessment recorded on or prior to the date of first study drug injection at Week 0 (Visit 2). For safety analyses, baseline and baseline period are defined as the last nonmissing assessment prior to the first injection of biologic rescue of ixekizumab 80 mg Q2W. For treatment-emergent adverse events (TEAEs) during biologic rescue with ixekizumab 80 mg Q2W, baseline is the event ongoing just prior to the first injection of biologic rescue of ixekizumab 80 mg Q2W; for TEAEs during other biologic rescue, baseline is the event ongoing just prior to the first injection of other biologic rescue (excluding ixekizumab 80 mg Q2W).

For IR Population, efficacy measures after initiation of biologic rescue of ixekizumab 80 mg Q2W will be summarized by originally assigned treatment group without inferential statistics. If sufficient patients took other biologic rescue after taking biologic rescue of ixekizumab 80 mg Q2W, additional efficacy summary may be provided.

The categorical safety measures will be summarized with incidence rates only.

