Nonrad-axSpA patients with objective signs of inflammation, defined as sacroiliitis on MRI and/or elevated CRP, are at increased risk of disease progression. In the present study sacroiliitis on MRI is defined by ASAS/OMERACT criteria (Rudwaleit et al. 2009b, 2009d) and elevated CRP is defined as CRP >5.00 mg/L. In addition, biologic treatment of patients with these objective signs of inflammation has been reported to result in consistently better clinical responses (compared with placebo) relative to the subpopulation of nonrad-axSpA patients with no evidence of sacroiliitis by MRI and a normal CRP level at baseline (Poddubnyy et al. 2012; Sieper et al. 2013; Sieper et al. 2015; Maksymowych et al. 2014). Therefore the following strata (positive MRI and elevated CRP; positive MRI and nonelevated CRP; negative MRI and elevated CRP) have been defined to ensure balance across treatment groups and greater comparability of treatment groups at baseline.

The Post-Study Follow-Up Period is important for safety monitoring following administration of the last study treatment. The duration of the Post-Study Follow-Up Period (Period 3) is approximately 12 weeks to allow for monitoring during ixekizumab clearance and reflects a time period equivalent to approximately 5 half-lives of ixekizumab.

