- Ixekizumab 80 mg Q2W inadequate responders will continue on the same regimen of ixekizumab 80 mg Q2W to allow more time to improve their response.

General treatment guidelines recommend a minimum period of 12 weeks to evaluate effect of biologic treatment modifications; however, if, in the opinion of the investigator, a patient does not show any clinical improvement after at least 8 weeks of the ixekizumab 80 mg Q2W rescue treatment, then the investigator may consider discontinuation of the patient from ixekizumab treatment. Such patients may then receive medical therapies as per local standard of care, which may include a TNF inhibitor, as prescribed by their physician, and are to remain in the study per the Schedule of Activities ([Appendix 2](#)). If an investigator decides to initiate a TNF inhibitor in

patients who fail rescue ixekizumab therapy, it is recommended that, for the timing of the first TNF inhibitor injection, investigators take into account the half-life of ixekizumab (approximately 13 days) and apply appropriate clinical judgement in balancing the need for treatment (eg, introducing a TNF inhibitor) with potential safety considerations. For patients who are prescribed a TNF inhibitor by the investigator after failing rescue ixekizumab therapy, the patient's specific TNF inhibitor may be provided to him/her during his/her participation in the trial up to Week 52 in an unblinded method either by direct supply or by reimbursement, depending upon local policy and procedures.

Details of the treatment regimens for patients responding to study treatment are summarized in [Table RHBX.2](#).

To maintain blinding throughout the study, each patient will receive at least 1 SC injection Q2W regardless of his/her assigned treatment regimen (that is, placebo will be administered every other week as necessary for the Q4W treatment group) until the patient discontinues investigational product.

The investigator or his/her designee is responsible for the following:

- explaining the correct use of the investigational product to the patient/patient caretaker
- verifying that instructions are followed properly
- maintaining accurate records of investigational product dispensing, collection, and administration
- returning all unused medication to Lilly or its designee at the end of the study

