### 6.13.1. Extent of Exposure

Duration of exposure to study drug will be summarized by treatment group for the Safety Population and IR Population during Period 2 using descriptive statistics.

A by-patient listing of exposure duration with number of active injections and total dose will be provided.

The duration of exposure on initially assigned treatment for the Safety Population will be calculated as:

*Date of last visit on initially assigned treatment (scheduled or unscheduled) or the first date of biologic rescue in Period 2 (for inadequate responders) – Date of first dose in Period 2+1*

Note that patients who are inadequate responders and therefore rescued by ixekizumab 80 mg Q2W during Period 2 will only have their exposure calculated up until the date of rescue.

The duration of ixekizumab exposure for IR Population will be calculated as:

*Date of last visit (scheduled or unscheduled) on or prior to ixekizumab treatment discontinuation in Period 2 –  
Date of first injection of biologic rescue of ixekizumab 80 mg Q2W+1*

The number and percentage of patients in the following categories will be included in the summaries as appropriate:

- >0, ≥7 days, ≥14 days, ≥30 days, ≥60 days, ≥90 days, ≥120 days, ≥150 days, ≥183 days, ≥210 days, ≥273 days and ≥365days. Note that patients may be included in more than 1 category.
- >0 to <7 days, ≥7 to <14 days, ≥14 to <30 days, ≥30 to <60 days, ≥60 to <90 days, ≥90 to <120 days, ≥120 to <150 days, ≥150 to <183 days, ≥183 to <210 days, ≥210 to <273 days, ≥273 to <365 days and ≥365 days.

The summaries will also include the following information:

- Total exposure in patient years, calculated as:

$$\text{Total exposure in patient years} = \frac{\text{Sum of duration of exposures for all patients in treatment group}}{365.25}$$

- Mean and median total dose. Total dose (in mg) is calculated by the number of active injections taken during the treatment period multiplied by dose.
  - For those randomized to ixekizumab 80 mg (Q2W or Q4W), the total dose (in mg) taken during Period 2 prior to biologic rescue of ixekizumab 80 mg Q2W will be calculated as:

*Total number of active injections (including loading doses, if any) received in Period 2 before biologic rescue of ixekizumab 80 mg Q2W x 80*

- For those patients receiving biologic rescue ixekizumab 80 mg Q2W, the total dose (in mg) on rescue ixekizumab will be calculated as:

*Total number of injections of biologic rescue of ixekizumab 80 mg Q2W x 80.*

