### **6.13.2. Adverse Events**

Adverse events (AEs) will be classified based upon the latest version of the MedDRA. Adverse events will be recorded at every study visit. Any condition starting on or after the date of informed consent will be considered an AE. Any preexisting condition which worsens in severity on or after the date of informed consent will be considered and recorded as an AE on the *Adverse Event (AE)* eCRF page from the date of worsening onwards.

A TEAE is defined as an event that first occurred or worsened in severity after baseline and on or prior to the date of the last visit within the defined treatment period. Both the date/time of the event and the date/time of the dose (that is, injection) are considered when determining TEAEs. Treatment-emergent AEs will be assigned to the study period to which it's considered treatment-emergent:

- The MedDRA Lowest Level Term (LLT) will be used when classifying AEs as treatment-emergent.
- The maximum severity recorded for each LLT prior to the first dose date/time in the treatment Period will be used as the pretreatment severity for that LLT. If an event during the baseline period has missing severity, and the event persists during the treatment period, then it will be considered as treatment-emergent, regardless of the postbaseline level of severity. Events with a missing severity during the treatment period will be considered treatment-emergent.

- Adverse events with a particular LLT will be classified as treatment-emergent if they first start on or after the first dose date/time in the treatment period (ie, a patient has no preexisting conditions with that LLT), or if the severity is greater than the pre-treatment severity for that LLT. If a partial AE start date/time is present, the date/time will be compared as far as possible to the treatment start date/time in order to determine whether the event is treatment-emergent or not. If there is any doubt, the event will be flagged as treatment-emergent.

A follow-up emergent adverse event (FEAE) is defined as an event that first occurred or worsened in severity after the date of Visit 15 (that is, Week 52) or the ETV:

- The MedDRA LLT will be used when classifying AEs as follow-up emergent.
- For AEs that are ongoing at the date of Visit 15 or ETV, the maximum severity recorded for each LLT on or prior to the date of Visit 15 or ETV will be used as the follow-up baseline severity for that LLT.

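### The SAP ends the rescue period by two rules that depend on a later switch of biologic, so some off-drug adverse events are neither treatment-emergent nor follow-up-emergent

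*SAP*

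**What the plan says.** - **Rescue period.** SAP 6.1.2.2 starts it at the first rescue injection, on or after Week 16. It "ends at the date of study treatment discontinuation for patients who did not initiate other biologic therapy, or at the start of other biologic treatment". The second end date applies to those who go on to another biologic. A separate other-biologic period then runs to Week 52 or the last visit, for switchers only.
- **Adverse event windows.** SAP 6.13.2 counts a treatment-emergent event (TEAE) if it arises or worsens after baseline and "on or prior to the date of the last visit within the defined treatment period". A follow-up-emergent event (FEAE) is one that "first occurred or worsened in severity after the date of Visit 15 (that is, Week 52) or the ETV".
- **Person-time.** For the Inadequate Responder (IR) Population, SAP 6.13.1 ends exposure at "Date of last visit (scheduled or unscheduled) on or prior to ixekizumab treatment discontinuation in Period 2", with no exception for switchers.
- **Continued follow-up.** Protocol 6.1 lets the investigator consider stopping rescue ixekizumab after at least 8 weeks without improvement. Such patients may receive other therapy and "are to remain in the study per the Schedule of Activities". Protocol 4.1 keeps anyone who stops treatment after Week 16 on the regular visits.
- **Reporting.** SAP 6.13.2 labels the IR window only as Period 2 after rescue begins, with no end date of its own. It does not list the other-biologic period. Protocol 9.5 says safety data after treatment discontinuation will be summarized separately.

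**The concern.** Whether an event counts as a rescue TEAE should depend on what had happened to the patient by the date of that event. Under SAP 6.1.2.2 it can depend on a decision taken afterwards. If the patient later starts another biologic, the off-drug interval is reclassified as rescue time. If not, the same interval belongs to no period until Week 52.

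Part of this interval falls while drug is still leaving the body. Protocol 6.1 gives a half-life of about 13 days, and Protocol 4.3 sets the 12-week follow-up "to allow for monitoring during ixekizumab clearance". Period 3 does not recover the events. An event still ongoing at Week 52 takes its maximum severity to date as the follow-up baseline, so it counts later only if it worsens. Period 3 is also not required when the last visit is more than 12 weeks after the last dose.

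At stake are the IR tables of TEAEs and of TEAE-based adverse events of special interest, with their exposure-adjusted rates. They carry the safety experience of patients moved from placebo to active drug and from Q4W to Q2W.

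**Working it through.** The plan states no figure on this point, so there is none to reproduce. The check sets the windows on one time axis, in study weeks.

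**Inputs**
- Rescue may start from Week 16 to Week 44 (Protocol 6.1).
- The earliest stop for no improvement is 8 weeks after rescue starts (Protocol 6.1).
- The FEAE window opens after Week 52 or the early termination visit (SAP 6.13.2).
- Scheduled visits fall at Weeks 16, 20, 24, 28, 32, 36, 44 and 52 (Protocol Appendix 2).

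**Unassigned time for a patient who starts no other biologic and stays to Week 52**

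Gap = 52 − (rescue start + 8)

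| Rescue start | Earliest stop | Gap (weeks) |
|---|---|---|
| 16 | 24 | 28 |
| 20 | 28 | 24 |
| 24 | 32 | 20 |
| 28 | 36 | 16 |
| 32 | 40 | 12 |
| 36 | 44 | 8 |
| 44 | 52 | 0 |

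The range is 0 to 28 weeks. A stop before 8 weeks for another reason, such as an adverse event, would lengthen it, to at most 52 − 16 = 36 weeks.

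**Two patients, with assumed dates.** Both start rescue at Week 16, stop at Week 24 and have the same non-serious event at Week 26. If the last injection was at Week 22, the event comes 28 days later, with 0.5^(28/13) = 0.22, or about 22%, of the drug remaining.
- *Patient A* starts a TNF inhibitor at Week 30. The rescue period runs to Week 30 and the last scheduled visit inside it is Week 28. The Week 26 event is a rescue TEAE.
- *Patient B* starts no other biologic. The rescue period ended at Week 24 and the FEAE window opens after Week 52. The event is neither.

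**Person-time in the same example.** IR exposure is 24 − 16 = 8 weeks for both. Patient A's event window is 28 − 16 = 12 weeks to the last scheduled visit, or 30 − 16 = 14 weeks if an unscheduled visit falls at the switch. Event window over person-time is 12/8 = 1.5, or at most 14/8 = 1.75. For Patient B it is 8/8 = 1.

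**The same boundary elsewhere in the SAP.** For immunogenicity, Table RHBX.6.10 follows every patient exposed to ixekizumab to the last visit and cuts earlier only if another biologic starts. For the Safety Population, SAP 6.1.2.1 runs Period 2 to Week 52 or early termination. Neither is cut at treatment discontinuation.

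**The case against.** The strongest reply is that SAP 6.13.2 describes the IR reporting window as Period 2 after rescue begins, and Period 2 ends at Week 52 or early termination. On that reading the events are counted. But the same section ties a TEAE to the defined treatment period, 6.1.2.2 defines that period, and a footnote to Table RHBX.6.1 says the IR safety summaries focus on time during rescue. The texts conflict and need reconciling; the label alone does not settle the matter.

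A second reply is that Protocol 9.5 meant off-drug events to be kept apart, so leaving them out of the rescue tables is by design. That is a fair account of the intent, but the SAP specifies no table to carry it out. It also does not explain why switchers' off-drug time is kept in.

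A reader might infer that these events disappear from all reporting. They do not:
- All adverse events are listed by patient (SAP 6.13.2).
- The SAE-by-preferred-term table in SAP 6.13.3 carries no explicit treatment-emergent condition.
- The registry output counts SAEs whether or not they are treatment-emergent (SAP 6.20).

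A reader might also infer that patients with infections are the ones whose events drop out, because an infection argues against starting a TNF inhibitor. That is possible, but nothing in the documents shows it.

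Two further limits stand. The revision history says too few patients took other biologics after rescue to analyse, so the group counted late is probably small. And a switcher's event counts only if a visit inside the period follows its onset.

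**Conclusion.** The inconsistency is real and lies in the stated rule. For patients who stop rescue ixekizumab, start no other biologic and remain in the study, non-serious adverse events and TEAE-based events of special interest up to Week 52 or early termination are neither TEAE nor FEAE. The same events can be rescue TEAEs for switchers. The interval is 0 to 28 weeks after the 8-week minimum. Switchers' exposure-adjusted rates set a longer event window over shorter person-time.

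This rests on reading the TEAE definition together with the period definition in SAP 6.1.2.2. The competing label in 6.13.2 is one of the passages to reconcile. The number of patients affected cannot be derived from the documents. A patient who leaves the study on stopping treatment has an early termination visit, so the gap is then short.

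The effect is confined to descriptive IR safety summaries, for which Table RHBX.6.2 plans no between-group comparison. The documents do not support extending it to the primary analysis or to the comparative safety analyses. The change should be made, but it is not critical to the trial's conclusions.

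**What to change.** In SAP 6.1.2.2, end the rescue period by one rule for every IR patient, so that an event is classified by what had happened by its own date. Either of these would do:

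1. The earlier of the start of another biologic and Week 52 or early termination, in line with Table RHBX.6.10.
2. Treatment discontinuation for all, optionally plus a fixed prespecified window that is cut at the start of another biologic.

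Use the same end date for IR person-time in 6.13.1 and for the exposure-adjusted rates in 6.13.2, and reword the IR reporting window in 6.13.2 to agree. Add the post-discontinuation safety summary promised in Protocol 9.5, with the other-biologic period shown separately, so that no Period 2 time is unassigned.

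A fixed window alone would not close the gap. With a last injection at Week 22 and a 12-week window, coverage ends at Week 34 and 52 − 34 = 18 weeks remain. Option 2 therefore needs the separate summary.

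The cost is SAP wording, one date derivation and one extra table. Option 1 also brings some off-drug events and person-time into the IR tables.
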